## **List of Abbreviations**

ACB – adductor canal block

IPACK – infiltration between the popliteal artery and capsule of the knee

FNB – femoral nerve block

TKA – total knee arthroplasty

PACU – post anesthesia recovery unit

DOSC – day of surgery center (preoperative area)

IV – intravenous

PO – per os (oral)

RASS – Richmond agitation sedation score

BPI – brief pain inventory

CONFIDENTIAL

This material is the property of Ochsner Clinic Foundation. Do not disclose or use except as authorized in writing by the study sponsor

## Study Summary

Title	Pain after total knee arthroplasty: a comparison of combined continuous adductor canal block with infiltration of local anesthetic between the popliteal artery and capsule of the knee block versus continuous adductor canal block alone on postoperative analgesia
Short Title	IPACK nerve block for total knee arthroplasty
Protocol Number	N/A
Phase	IV
Methodology	Allocation: Randomized Endpoint Classification: Efficacy Study Intervention Model: Single Group Assignment Masking: Double Blind (Outcomes Assessor, patient) Primary Purpose: Treatment
Study Duration	Intervention period immediately prior to surgery with follow-up until hospital discharge
Study Center(s)	Ochsner Medical Center Main Campus
Objectives	To examine the effect of two approaches to nerve blockade on opioid consumption, patient satisfaction, postoperative pain, mobility, length of hospital stay, and several other secondary outcomes.
Number of Subjects	72 total, approximately 36 in each study arm
Diagnosis and Main Inclusion Criteria	
Inclusion Criteria:
 
 
• Unilateral, primary tricompartment total knee arthroplasty
 
• Age 18 years or older
 
• ASA I-III
 
• Eligible for spinal or combined spinal epidural anesthetic
 
• Able to speak, read, and understand English
 
• Willing to participate in the trial
 
• Anticipated discharge home from hospital
 
 
Exclusion Criteria:
 
 
• Contraindication to regional anesthesia or peripheral nerve blocks
 
• Allergy to local anesthetics
 
• Allergy to NSAIDs
 
• Chronic renal insufficiency with Cr > 1.4 or GFR < 60
 
• Have chronic pain that is not related to their knee joint
 
• Have been using opioids on a chronic basis (daily or almost daily opioid use for 3 months or longer)
 
• Have a pre-existing peripheral neuropathy involving the operative site
 
• Body mass index greater than 40
 

Study Regimen	Double-blind, randomized controlled clinical trial to test the efficacy of IPACK on postoperative opioid consumption, patient satisfaction, pain scores, mobility, and several other secondary outcomes in adults undergoing primary unilateral TKA. Enrolled patients will be randomized to either continuous ACB with IPACK or to continuous ACB with sham subcutaneous saline injection. Outcomes assessors and patients will be blinded to the intervention.
Duration of administration	Single preoperative IPACK block
Reference therapy	No IPACK block/sham subcutaneous saline injection
Statistical Methodology	Descriptive statistics per Ochsner statisticians

CONFIDENTIAL

This material is the property of Ochsner Clinic Foundation. Do not disclose or use except as authorized in writing by the study sponsor

# 1 Introduction

This document is a protocol for a human research study. This study is to be conducted according to US and international standards of Good Clinical Practice (FDA Title 21 part 312 and International Conference on Harmonization guidelines), applicable government regulations and Institutional research policies and procedures.

## 1.1 Background

Total knee arthroplasty (TKA) is an effective surgical treatment for end-stage knee osteoarthritis and is commonly performed in the United States. Recovery following TKA is painful and regional anesthesia is often utilized to minimize postoperative pain, improve function, and allow earlier rehabilitation physical therapy. Goals of regional anesthesia are to provide effective analgesia with minimal postoperative muscle weakness to allow for early postoperative rehabilitation while also minimizing fall risk in the immediate postoperative period. While many different regional modalities exist and are effective for improving pain control, there is no consensus for best technique. Popular regional techniques for postoperative analgesia include single injection or continuous femoral nerve block (FNB) and adductor canal block (ACB), sciatic nerve block (SNB), and lumbar epidurals. Each modality requires a technical skill set and has its own limitations, benefits, and risk profile. Interestingly, a study in 2014 showed that approximately 76% of TKA surgeries across the country are still performed under general anesthesia and 87% of these patients do not receive any regional technique, despite overwhelming evidence of improved patient outcomes, decreased length of hospital stay, and improved function with regional techniques. More recently, a 2016 study showed that only 27.3% of patients in a national registry received a peripheral nerve block and this was associated with decreased extended-length recovery room stays and postoperative nausea and/or vomiting.

Recent studies published, including one study performed at Ochsner Medical Center, support that ACB provides similar analgesia compared to FNB while preserving straight leg raise and sparing the majority of quadriceps motor function. Both ACB and FNB only provide analgesia to the anterior medial part of the knee and most tricompartment TKA patients require supplemental opioid medications to cover joint pain usually attributed to the sciatic and obturator nerves. Historically SNB was used effectively to provide posterior analgesia but now is less used due to concern over increased difficulty with physical therapy due to foot drop. Because peroneal nerve palsy occurs in 0.3-1.3% of TKA, an additional concern is that foot drop due to SNB may mask surgical injury to the common peroneal nerve.

A novel alternative to SNB is the infiltration of local anesthetic between the popliteal artery and capsule of the knee (IPACK) block that targets the terminal sensory nerve endings to the posterior knee joint. Common practice at our institution incorporates preoperative continuous ACB and single IPACK block. A retrospective review of patients at our institution who received IPACK block with continuous FNB compared to patients who received FNB alone showed similar VAS pain scores with significantly decreased narcotic requirements postoperatively. The same retrospective review showed that patients who received IPACK block with continuous ACB had clinically improved performance with physical therapy and a significantly shorter hospital stay. The goal of this study is to prospectively examine and hopefully confirm the observations of the retrospective chart review by studying the effect of preoperative IPACK

CONFIDENTIAL

This material is the property of Ochsner Clinic Foundation. Do not disclose or use except as authorized in writing by the study sponsor

block on opioid consumption, patient satisfaction, pain scores, walk distance, hospital length of stay, and several other secondary outcomes.

## **1.2 Investigational Agent**

Infiltration of local anesthetic between the popliteal artery and capsule of the knee (IPACK) block using 20ml of ropivacaine 0.25% with 1:300,000 epinephrine.

## **1.3 Preclinical Data**

N/A

## **1.4 Clinical Data to Date**

No published studies about IPACK exist. An IRB-approved retrospective review of patients at our institution who received IPACK with continuous FNB compared to patients who received FNB alone showed similar VAS pain scores with significantly decreased narcotic requirements postoperatively. The group of patients who received IPACK block had a 38.8% decrease in the mean opioid consumption in the first 24 hours. The same retrospective review showed that patients who received IPACK with continuous ACB had clinically improved performance with physical therapy and a significantly shorter hospital stay.

## **1.5 Dose Rationale and Risk/Benefits**

We chose 20ml of 0.25% ropivacaine with 1:300,000 epinephrine to use for the IPACK because under ultrasound guidance it appears to provide adequate spread without reaching the sciatic nerve and causing foot drop. Less volume may not reliably provide analgesia. Larger volumes could cause foot drop or even lead to anesthetic toxicity.

# **2 Study Objectives**

The goal of this study is to prospectively examine the effect of preoperative IPACK block on opioid consumption, patient satisfaction, pain scores, walk distance, hospital length of stay, and several other secondary outcomes.

# **3 Study Design**

## **3.1 General Design**

Double blinded, randomized controlled trial. All patients who present for primary, unilateral tricompartment TKA will be screened for inclusion. Consecutive patients who meet preset inclusion and exclusion criteria will be recruited either on day of surgery or in the preoperative anesthesia clinic by one of the study investigators. Written consent will be obtained for study participation. Patients who participate will be randomized into one of two treatment arms: continuous ACB with IPACK block versus continuous ACB with sham subcutaneous saline injection. Randomization will be done using the website random.org's Coin Flipper, selecting the Susan B Anthony coin, and flipping 5 coins. Majority heads will be randomized to receive the IPACK block whereas majority tails will be randomized to receive the sham subcutaneous injection. See Attachment A for an example of this website.

CONFIDENTIAL

This material is the property of Ochsner Clinic Foundation. Do not disclose or use except as authorized in writing by the study sponsor

Only the regional anesthesiologist performing the block will know the randomization status. The study participants, outcome assessors/researchers, other anesthesia personnel, surgeons, physician assistants, and nurses will be blinded to the treatment arm. All patients will receive sedation with midazolam and/or fentanyl titrated to comfort during block procedures. Per our standard practice at Ochsner Medical Center, all patients will have either spinal or combined spinal-epidural anesthesia with mepivacaine 1.5% as the primary anesthetic during the surgery and sedation with propofol titrated to comfort. Also per our standard practice at Ochsner Medical Center, multimodal therapy will include ketamine 0.25mg/kg IV (up to 50mg) intraoperatively, dexamethasone 8mg IV intraoperatively, pregabalin 150mg PO preoperatively (adjusted to 75mg for age over 70) followed by 75mg nightly (or home gabapentin dose), acetaminophen 1000mg IV followed by 100mg PO every 6 hours postoperatively, and celecoxib 400mg PO on POD #0 followed by 200mg PO daily.

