### **3.2 Primary Study Endpoints**

- Cumulative opioid consumption (morphine equivalents) in the first 24 hours

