### **5.5 Subject Compliance Monitoring**

Study investigators will ensure that correct multimodal therapy is ordered and review the medication record to ensure appropriate administration by nursing.

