## **7 Statistical Plan**

### **7.1 Sample Size Determination**

Prior published literature demonstrates analgesic equivalence between adductor canal block and femoral nerve block. An institutional retrospective study here showed a 38.8% effect difference between femoral nerve block with and without IPACK. Using this information, for an effect size of 0.4, power of 0.8, and significance level of 0.05 we determined a sample size of 64 patients. Assuming a dropout rate of 10%, we will include 72 patients in this study with approximately 36 patients per study arm.

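### Section 3.1 steps acetaminophen down ten-fold from the IV to the oral dose, and nothing in the documents explains or confirms the step in a regimen that investigators must check

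*Combined protocol and SAP*

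**What the plan says.** Section 3.1 (General Design) sets out the co-analgesic drugs for every participant. It introduces them with "Also per our standard practice at Ochsner Medical Center, multimodal therapy will include" and makes no distinction between the arms. Three drugs in that sentence have a first dose and a follow-on dose:

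- Acetaminophen: "acetaminophen 1000mg IV followed by 100mg PO every 6 hours postoperatively".
- Celecoxib: "celecoxib 400mg PO on POD #0 followed by 200mg PO daily".
- Pregabalin: "pregabalin 150mg PO preoperatively (adjusted to 75mg for age over 70) followed by 75mg nightly (or home gabapentin dose").

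Ketamine and dexamethasone are also listed, each with an intraoperative dose only.

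Section 5.5 (Subject Compliance Monitoring) gives the duty that goes with the regimen: "Study investigators will ensure that correct multimodal therapy is ordered and review the medication record to ensure appropriate administration by nursing". It does not restate any dose.

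The primary endpoint in Section 3.2 is "Cumulative opioid consumption (morphine equivalents) in the first 24 hours". Section 7.2 names a t-test for comparing the arms and specifies no adjustment for co-analgesic exposure.

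**The concern.** The oral acetaminophen figure stands ten-fold below the IV figure for the same drug in the same clause, and the protocol gives no reason for a reduction of that size. The two figures differ by exactly one digit place, so a transcription slip is possible, but the documents cannot show whether there was one.

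The sentence is not background narrative. It is the only place where these doses are written down, and it states what patients will receive. Someone carrying out the Section 5.5 check has no other figure in the protocol to check against. If the printed oral figure is not the one intended, there are two ways for it to cause trouble. Staff may follow the print, and patients then receive an unintended dose. Or some staff may follow the print and others the usual local order, and delivery is then inconsistent.

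At stake are patients' pain control, the level and spread of opioid use in the primary window, and a reader's ability to know what background analgesia the IPACK block was tested against.

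**Working it through.** No sample size, power or alpha figure is involved. The check has three parts.

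**1. Step ratios (follow-on dose divided by first dose), all from Section 3.1**

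| Drug | First dose | Follow-on dose | Ratio |
|---|---|---|---|
| Acetaminophen | 1000 mg IV | 100 mg PO every 6 h | 100/1000 = 0.1 |
| Celecoxib | 400 mg PO | 200 mg PO daily | 200/400 = 0.5 |
| Pregabalin, age 70 or under | 150 mg PO | 75 mg PO nightly | 75/150 = 0.5 |
| Pregabalin, age over 70 | 75 mg PO | 75 mg PO nightly | 75/75 = 1 |

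For a patient continued on a home gabapentin dose, no pregabalin ratio can be formed. Acetaminophen is the only one of the three drugs that also changes route.

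**2. Oral total over 24 hours as printed**

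- Doses per 24 h = 24/6 = 4.
- Total = 4 × 100 mg = 400 mg, against 1000 mg for the single IV dose.

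This describes the printed schedule. It is not the exposure within the primary endpoint window. The documents do not give the time of the IV dose, the start of oral dosing, or the event that starts the 24-hour clock, so the number of oral doses inside the window, and whether the IV dose falls inside it, cannot be derived.

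**3. Search for a second statement**

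- The study summary, Section 5.2 (Treatment Regimen), Section 5.6 (Prior and Concomitant Therapy) and Section 6 (Study Procedures) do not mention acetaminophen.
- Section 5.5 refers to multimodal therapy without doses.

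Section 3.1 is therefore the only source, and no other place in the text confirms or corrects the figure.

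**The case against.** The strongest reply is that the documents do not contradict themselves. The two figures differ in route and time, no other section gives another oral dose, and no stated total fails to add up. Nothing in the protocol says that step ratios should match across drugs, and the comparison pattern is weak: only celecoxib halves without conditions. All of this stands. It means that the documents cannot prove the figure wrong. It does not mean that they confirm it, and a figure with a single source and no explanation still needs confirming when investigators are asked to check against it.

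The reply also limits what may be inferred. Four stronger readings are tempting:

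- *That the figure drives the primary endpoint.* The documents give no estimate of acetaminophen's effect on opioid use and do not place its doses relative to the 24-hour window. The supportable statement is that it can affect opioid use.
- *That it biases the comparison.* The regimen is the same in both arms, so the printed figure does not in itself favour either.
- *That every patient would be logged as a deviation.* Section 5.5 asks for the order and the medication record to be reviewed. It sets up no deviation log and does not name Section 3.1 as its standard. Since Section 3.1 presents the regimen as existing institutional practice, the therapy to be ensured could be read as that practice.
- *That the figure is certainly a typing error.* This would need knowledge from outside the documents.

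**Conclusion.** The point holds as a request to reconcile. The oral acetaminophen figure in Section 3.1 is one tenth of the IV figure, the step is unexplained and stated only once, and it belongs to a regimen written for all 72 planned patients that investigators must see correctly ordered and given. The number of patients who would actually receive an unintended dose is unknown. It depends on whether the printed figure is intended and, if it is not, on whether staff follow it.

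The consequence for the primary endpoint is possible but not measurable from the documents. A common change in co-analgesia could shift the overall level of opioid use. Inconsistent delivery could widen its spread, and the planned t-test names no adjustment that would absorb this. Randomization, the between-arm contrast and the sample size are untouched.

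The conclusion rests on one assumption: that no explanation stands in the pages or attachments not available to this review. It is worth correcting before enrolment because the error, if it is one, concerns a dose given to patients and costs almost nothing to remove.

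**What to change.** 1. The sponsor should reconcile the IV and oral acetaminophen figures in Section 3.1 with the institutional standard practice that the section cites, and confirm or correct the sentence. This review does not say which figure is right and proposes no dose.
2. Issue the confirmed sentence with IRB notification, and have Section 5.5 cite it as the reference for the check of orders and medication records.
3. If any patient has already been treated, record the acetaminophen dose actually given, so that any variation in background analgesia can be described alongside the primary result.

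The cost is a one-line protocol correction, a cross-reference in Section 5.5 and, where patients have already been treated, a look at their medication records, which Section 5.5 already has investigators review. Neither the design nor the sample size changes.

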### **3.2 Primary Study Endpoints**

- Cumulative opioid consumption (morphine equivalents) in the first 24 hours

### **3.3 Secondary Study Endpoints**

- Patient satisfaction on day of discharge using the Brief Pain Inventory (BPI) or a similar validated satisfaction survey
- Average pain score at rest and with physical therapy in PACU, POD#1 am, POD#1 pm
- Worst pain score at rest and with physical therapy in PACU, POD#1 am, POD#1 pm
- Walk distance on POD#1 am, POD#1 pm, POD#2
- Time to first intravenous opioid, oral opioid in PACU and after arrival to hospital room
- Time to oral-only opioids
- Pain location
- Hospital length of stay
- Incidence of foot drop
- Incidence of itching, nausea, or vomiting in PACU, POD#1am, POD#1 pm
- Incidence of over-sedation based on Richmond Agitation Sedation (RASS) score

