## **4.4 Early Withdrawal of Subjects**

### **4.4.1 When and How to Withdraw Subjects**

Patients may voluntarily withdraw at any time of the study. All procedures are performed preoperatively and further patient participation only includes questionnaires while admitted to the hospital. Patients may refuse to answer these questionnaires. Patients may also elect to discontinue their continuous ACB early.

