### **4.4.2 Data Collection and Follow-up for Withdrawn Subjects**

All withdrawn subjects will be included in the intention to treat analysis. Already-accrued data for individuals who withdraw from the study will be maintained as part of the study data.

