### **7.2 Statistical Methods**

A t-test will be used to compare the two arms of the study. We will apply other statistical methods as per Ochsner's statistics team & researchers.

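### Pain and walk distance are measured repeatedly, but no analysis is named that uses a patient's other scores when one is refused (secondary endpoints, minor)

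*Combined protocol and SAP*

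**What the plan says.** Section 3.3 lists two pain outcomes, each under two conditions and at three times: "Average pain score at rest and with physical therapy in PACU, POD#1 am, POD#1 pm" and "Worst pain score at rest and with physical therapy in PACU, POD#1 am, POD#1 pm". It also lists "Walk distance on POD#1 am, POD#1 pm, POD#2".

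Section 7.2 gives the analysis in two sentences: "A t-test will be used to compare the two arms of the study", followed by "We will apply other statistical methods as per Ochsner's statistics team & researchers". The Study Summary offers only "Descriptive statistics per Ochsner statisticians". No section names a repeated-measures model, a summary measure, a key time or a method for missing scores.

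Two passages bear on missing data. Section 4.4.1 says "Patients may refuse to answer these questionnaires". Section 4.4.2 says "All withdrawn subjects will be included in the intention to treat analysis" and keeps the data already collected, but it does not say how a missing score enters that analysis. Section 9.3 asks that missing data be explained on the case report form, which is a recording rule. Section 6.2 adds that patients who reach the discharge milestones go home on the afternoon of POD#1.

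**The concern.** Each patient can give up to three values of every pain measure, and those values will be correlated. If the one named test is applied at each time, each comparison uses one score per patient and ignores the rest. A patient who answers in the morning and refuses in the afternoon then contributes nothing to the afternoon comparison, although the morning score says something about the missing one.

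If patients in more pain in the morning refuse more often in the afternoon, the arm with more pain loses more of its high scores, and the afternoon difference shrinks. Pain and walking are among the aims in section 2, and the trial is small, so recorded scores should not be wasted. A named model would also give the intention-to-treat statement in section 4.4.2 a working meaning for these outcomes.

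**Working it through.** The plan gives no figure on this point to reproduce. The check asks what per-time t-tests would lose.

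**Inputs from the documents.** There are three pain times, two pain measures and two conditions (3.3), three walk occasions (3.3), and 64 evaluable patients of 72 enrolled (7.1), so 32 per arm. Refusal is allowed, but no rate is given (4.4.1).

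**Assumptions, because the documents give no values.** The correlation between POD#1 morning and afternoon scores is 0.5 (range 0.4 to 0.7), or 0.6 in the refusal simulation. The pain SD is 2.5 points. Refusal is 15% or 30%.

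**1. Count.** Pain gives 2 × 2 × 3 = 12 comparisons and walking gives 3, so 15 if each is tested separately.

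**2. Complete data.** A t-test at one time keeps its type I error. A mixed model with arm, time, arm-by-time and unstructured covariance gives the same difference at each time, with essentially the same standard error. Nothing is lost here.

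**3. Scores missing completely at random.** The variance of one time's arm difference, relative to full data on three occasions at correlation 0.5, is:

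| Missing per occasion | Per-time t-test, 1/(1 − p) | Mixed model |
|---|---|---|
| 10% | 1.11 | 1.08 |
| 20% | 1.25 | 1.18 |

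The gain is modest: 1.08/1.11 = 0.97 and 1.18/1.25 = 0.94.

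**4. Refusal that follows earlier pain.** I simulated 8,000 trials per row with 32 per arm and a true benefit of 1.0 point at both times. All morning scores were observed. Afternoon refusal was logistic in the morning score. The likelihood estimate of each arm's afternoon mean is (mean of observed afternoon scores) + b × (mean of all morning scores − morning mean of responders), where b is the pooled within-arm slope.

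| Refusal | Slope per point | t-test estimate | Likelihood estimate | SE of t-test | Bias / SE | RMSE, t-test vs likelihood |
|---|---|---|---|---|---|---|
| 15% | 0.3 | 0.97 | 1.00 | 0.67 | 0.04 | 0.67 vs 0.66 |
| 15% | 0.6 | 0.91 | 1.00 | 0.66 | 0.14 | 0.66 vs 0.66 |
| 30% | 0.3 | 0.95 | 1.00 | 0.74 | 0.07 | 0.74 vs 0.71 |
| 30% | 0.6 | 0.87 | 1.01 | 0.72 | 0.18 | 0.73 vs 0.71 |

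**5. Averaging POD#1 morning and afternoon.** The SE relative to one time is √((1 + ρ)/2). At ρ = 0.5 this is √0.75 = 0.866, which is 13% smaller (16% at ρ = 0.4, 8% at ρ = 0.7). With 0.5 SD at both times and 32 per arm, power is 0.50 for one time. For the average it is 0.62 at ρ = 0.5 (0.65 at 0.4, 0.57 at 0.7).

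The gain depends on the effect lasting. With 0.5 SD in the morning and x SD in the afternoon, the average beats the morning alone only if (0.5 + x)/2 ÷ 0.866 > 0.5, so x > 2 × 0.5 × 0.866 − 0.5 = 0.37. At x = 0.2 the standardised mean effect is 0.35/0.866 = 0.40, and power is 0.36 against 0.50 for the morning alone.

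**The case against.** The strongest reply is that the plan never says it will run t-tests on pain or walking. That stands. A reader might infer from section 7.2 a decision to use separate t-tests on repeated data, but the sentence names no endpoint or time and the next one defers other methods. The documents support only this: the analysis is unspecified, with a t-test as the one named default.

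Three other stronger readings also fail.

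- **Refusing one questionnaire removes the patient.** A per-time test loses that patient at that time only. Complete-case analysis over all times would lose more, but no section proposes it, and section 4.4.2 keeps data already collected.
- **Separate t-tests are invalid or needlessly imprecise at each time.** Step 2 shows otherwise with complete data, and step 3 shows a small loss when scores are missing at random.
- **Modelling the correlation by itself brings the 13% gain.** That gain comes from averaging two times. A t-test on each patient's two-time mean has the same precision when both scores are present, and the gain can turn into a loss, as step 5 shows.

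It is also fair that the bias in step 4 is small beside the standard error and rests on assumed refusal patterns. Walk distance is not described as a questionnaire item, so the refusal argument does not clearly reach it. What remains is that no method is named for the repeated outcomes, and a cheap one exists that uses all recorded scores.

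**Conclusion.** The point holds as a minor one. The repeated outcomes have no named analysis that uses the other scores of a patient who refuses a questionnaire. If the t-test were applied time by time, the estimates would be valid with complete data, slightly less precise with scores missing at random, and 3% to 13% too small in the refusal scenarios examined. That bias is 0.04 to 0.18 standard errors. These figures depend on the assumed correlation, SD, refusal rate and strength of dependence.

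The clearer missing-data problem for walking is on POD#2. Under the discharge practice in section 6.2, those values would come mainly from slower patients, so the missingness is related to the outcome itself.

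Only secondary endpoints are affected. The primary endpoint in section 3.2 is one 24-hour total per patient.

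**What to change.** In section 7.2:

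- For each of the four pain measures (average or worst, resting or during therapy), name one linear mixed model with arm, time, arm-by-time and unstructured covariance. Include every patient with at least one score, and report the arm difference at each time with its interval.
- Optionally pre-specify the POD#1 morning and afternoon average as a summary for each measure, always beside the time-specific differences. Note that it loses power if the effect of the single injection fades.
- Use the same model for POD#1 morning and afternoon walk distance.
- Treat POD#2 walk distance separately. Report how many patients in each arm were still in hospital, and say that the values describe only those patients.
- Do not adjust for hours from block to assessment. It arises after randomisation, and no section says it is recorded.
- Tabulate refusals by arm and time.

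The cost is a few lines of text and a little programming, with no new visits or staff. The downside is that the model assumes missing scores can be explained by the observed ones, which the data cannot confirm. The model also does not settle multiplicity across the measures.

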## **6.2 Postoperative Course**

No further procedures are required.

At 24 hours, the cumulative opioid consumption will be summated. An outcomes assessor will survey the patient at pre-specified times for secondary outcomes. Additional secondary outcomes will be pulled from the electronic medical record.

Per standard of care at Ochsner Medical Center, patients that meet clinical milestones will be discharged home on the afternoon of POD#1 with an on-Q pain ball that will be removed by the patient after approximately 48 hours.

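### POD#2 walk distance and time to first IV opioid are observed only in subsets formed after randomisation, and the plan does not say how the other patients are counted

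*Combined protocol and SAP*

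**What the plan says.** Section 3.3 lists among the secondary endpoints "Walk distance on POD#1 am, POD#1 pm, POD#2" and "Time to first intravenous opioid, oral opioid in PACU and after arrival to hospital room".

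Three places fix when these can be observed. Section 6.2 states that "patients that meet clinical milestones will be discharged home on the afternoon of POD#1". The study-duration entry of the Study Summary reads "Intervention period immediately prior to surgery with follow-up until hospital discharge". Section 4.4.1 says that "further patient participation only includes questionnaires while admitted to the hospital". Section 6.2 also takes some secondary outcomes from the electronic record, but nothing provides for measuring walking at home.

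On analysis, section 7.2 says "A t-test will be used to compare the two arms of the study" and continues "We will apply other statistical methods", leaving the choice to the statistics team and researchers. The Study Summary mentions descriptive statistics only.

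The nearest rules lie elsewhere. Section 4.4.2 keeps withdrawn subjects in the intention-to-treat analysis, section 9.3 says how to mark blanks on the case report form, and section 8.1 sets a 30-day window for adverse events.

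**The concern.** A patient who goes home as planned on POD#1 has not withdrawn, yet has no POD#2 walk distance. A patient who never needs an IV opioid has no time to first IV opioid. Both states arise after randomisation, and the treatment may affect both.

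If the plan is carried out by comparing whatever values exist, each comparison is made in a subset selected by a post-randomisation event. Should IPACK speed discharge or let more patients avoid IV opioid, the patients who do best leave the comparison and a benefit is understated. Should it delay discharge, the walk difference is distorted the other way. Walk distance is named among the objectives in section 2. With no rule written down, the handling could also be chosen after the unblinding that section 8.4 places at the end of the study.

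**Working it through.** **Step 1: who can have a value.** Set side by side, section 6.2 (home on POD#1 afternoon), the Study Summary (follow-up to discharge) and section 4.4.1 (participation only while admitted) leave POD#2 distance observable only in those still in hospital. POD#1 am walk comes before the afternoon discharge and is available for all. POD#1 pm walk is available for all only if it is taken before discharge, which is not stated. None of sections 4.4.2, 7.2, 8.1 and 9.3 says how discharged patients or non-users are counted.

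**Step 2: size for walk distance.** No figure in the plan bears on this directly. The one input from the documents is 36 patients per arm (section 7.1). Everything else is assumed:
- true POD#2 benefit of 0.5 SD;
- 50% of controls discharged before POD#2;
- discharge readiness and walking jointly normal with correlation r;
- IPACK shifts readiness by s SD, and patients with readiness below c = 0 stay.

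With φ and Φ the normal density and distribution function, the difference among those remaining is

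0.5 − r × [φ(c−s)/Φ(c−s) − φ(c)/Φ(c)], where φ(0)/Φ(0) = 0.3989/0.5 = 0.798.

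- s = 0: the bracket is 0.
- s = 0.25: 0.3867/0.4013 = 0.964, bracket 0.166. IPACK remaining: 36 × 0.4013 = 14.4.
- s = 0.5: 0.3521/0.3085 = 1.141, bracket 0.343. IPACK remaining: 36 × 0.3085 = 11.1.
- s = −0.25 (IPACK delays discharge): 0.3867/0.5987 = 0.646, bracket −0.152. IPACK remaining: 36 × 0.5987 = 21.6.

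| Shift s | r = 0.5 | r = 0.8 | r = 1.0 | Remaining, control v IPACK |
|---|---|---|---|---|
| 0 | 0.50 | 0.50 | 0.50 | 18 v 18 |
| 0.25 | 0.42 | 0.37 | 0.33 | 18 v 14 |
| 0.5 | 0.33 | 0.23 | 0.16 | 18 v 11 |
| −0.25 | 0.58 | 0.62 | 0.65 | 18 v 22 |

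Units are full-population SDs. At r = 0 the difference stays 0.50 whatever the shift. Letting control discharge run from 30% to 80%, with r between 0.5 and 0.8, gives 0.34-0.43 at s = 0.25 and 0.18-0.36 at s = 0.5.

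**Step 3: precision when there is no bias.** With s = 0, simulated power of a t-test among the 18 v 18 remaining is about 31%, 35%, 46% and 66% at r = 0, 0.5, 0.8 and 1.0. It is about 55% if all 36 per arm were measured. Fewer patients remain, but selection also narrows the spread, so the net effect on power depends on r.

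**Step 4: time to first IV opioid.** Assume exponential times on one 24 h clock and a hazard ratio of 0.5. With control non-use p, the control rate is λ = −ln(p)/24 and the IPACK rate is λ/2. For each arm's own rate λ, the users-only mean is 1/λ − 24e^(−24λ)/(1 − e^(−24λ)) and the restricted mean over all patients is (1 − e^(−24λ))/λ.
- p = 10%: IPACK non-use is √0.10 = 32%. Users-only means are 9.7 and 7.8 h, a difference of 2.0 h. Restricted means are 14.3 and 9.4 h, a difference of 4.9 h.
- p = 50%: IPACK non-use is √0.50 = 71%. The users-only difference is 0.7 h and the restricted-mean difference is 3.0 h.

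At hazard ratio 1 both differences are zero. The two quantities are different estimands: the users-only one leaves out the benefit of never needing the drug.

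**The case against.** The strongest reply is that the plan never commits to the faulty analysis. The t-test in section 7.2 is attached to no endpoint, follows a sample-size section built on opioid consumption, and is followed by an open door to other methods. That stands: a reader might infer that times to first opioid will be t-tested among users, but the text does not say so. What remains is that no rule exists.

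A reader might also infer that IPACK will shorten stay, and so that the benefit will be understated, because sections 1.1 and 1.4 report a shorter stay with IPACK plus continuous ACB. Neither section names the comparator for that result, and section 3.1 gives continuous ACB to both arms. The documents therefore do not support a direction.

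The figures can be challenged too, since every input apart from 36 per arm is assumed. Quoting only 31% against 55% power would pick the least favourable correlation. Measured against the narrower spread of the remaining patients, the difference at a 0.25 SD shift is about 0.46-0.58, little or no loss. Clear standardised loss appears only at the 0.5 SD shift (about 0.36 down to 0.28). The 24 h clock in step 4 is also simpler than the two listed periods, PACU and hospital room. These points stand, and the numbers serve as illustration only.

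Finally, the reach is small: one of three walk time points, plus opioid timing. That is correct, and it sets the weight of the point.

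**Conclusion.** The gap is real and minor. The schedule leaves POD#2 walk distance observable only in patients still in hospital, time to first IV opioid has a value only for users, and the plan does not say how the others are counted. A comparison of observed values would be biased if IPACK changes discharge or IV opioid use: toward understating a benefit if it speeds discharge or avoids IV opioid, the other way if it delays discharge. If discharge does not differ by arm, the walk difference is unbiased.

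The size cannot be known from the documents, which give no discharge or non-use rates. Under the assumptions above, a true 0.5 SD walking benefit appears as anything from 0.50 SD (no shift) to 0.16 SD (0.5 SD shift, correlation 1.0). The primary endpoint, length of stay and POD#1 am walk distance are not affected.

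**What to change.** In sections 3.3 and 7.2:

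1. Make POD#1 walk distance the formal mobility comparison: POD#1 am, and POD#1 pm if it is recorded before discharge. Report POD#2 distance descriptively, with the number remaining in each arm.
2. Analyse time to first IV opioid, and to first oral opioid if there are non-users, in all randomised patients by Kaplan-Meier and log-rank. State time zero for each listed period (PACU arrival; hospital-room arrival). Censor non-users at the end of that period's observation: PACU transfer for the first; for the second, discharge or a stated earlier cut-off before the POD#1 afternoon discharge. An earlier cut-off has the advantage that censoring does not depend on how fast a patient recovers. Report the proportion never using the drug in each arm.

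The cost is a few lines of text and a note of whether the POD#1 pm walk preceded discharge. The downside is that POD#2 distance is no longer a formal comparison.
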